### Recruitment

- Recruitment data will be summarized in a flow diagram.

### Screening data

- Screening data will be summarized to for each study group. Eligibility criteria are specified in protocol section 4.2 and section 4.3.

### Withdrawal and follow-up

- Withdrawal of individual subjects is described in protocol section 8.4. Should reasons for withdrawal be known, these will be described, including the timing of withdrawal.

### Baseline patient characteristics

- Demographic data will be summarized by descriptive statistics per dose group and will include the total number of observations (n), plus the mean, standard deviation (SD) and range for normally distributed continuous variables and number and percentages for dichotomous variables. This data will be tabulated.
- Where applicable, continuous outcomes that are not normally distributed will be transformed using a suitable transformation before reporting means and SDs. Where a suitable transformation cannot be found, the mean and SDs will be substituted with the median and interquartile ranges. For discrete (or count) data we will report the medians and interquartile ranges. Binary data will be presented as counts and proportions.

**Analyses in relation to endpoints**

**Safety outcome analyses:**

- For each solicited (local or general) adverse event type, the number and proportion of subjects experiencing that AE within the Protocol-defined timeframe will be tabulated by severity grade for each dose group and for the entire study population. This will also be tabulated for subjects experiencing any solicited local, any solicited general and any solicited AE (see example table below). Where applicable, we will compare these proportions between groups. Relatedness (possibly, probably or definitely) of solicited AEs to TB31F administration may also be presented. (Outcome measures 1 and 2).
- For each unsolicited adverse event type (categorized by ICD-10), the number of events per dose group and overall study population will be described categorized by severity grade and relation to TB31F administration. (Outcome measure 4).
- The proportion of individuals with grade 1, 2 and 3 adverse events may be compared between groups (Outcome measures 1,2,4) .
- The total number of grade 1, 2 and 3 adverse events as count data may be compared between groups.
- Individual serious adverse events (SAEs) will be summarized, including relatedness to TB31F administration (Outcome 5).
- Withdrawals due to AEs/SAEs will be summarized per group.

Table - Descriptive statistics for subjects experiencing solicited AEs

|               |           | Group 1   |   | Group 2   |   | Group 3   |   | Group 4   |   | Group 5   |   | All       |   |
|---------------|-----------|-----------|---|-----------|---|-----------|---|-----------|---|-----------|---|-----------|---|
|               |           | #Subjects | % | #Subjects | % | #Subjects | % | #Subjects | % | #Subjects | % | #Subjects | % |
| Local AE1     | Grade 1   |           |   |           |   |           |   |           |   |           |   |           |   |
|               | Grade 2   |           |   |           |   |           |   |           |   |           |   |           |   |
|               | Grade 3   |           |   |           |   |           |   |           |   |           |   |           |   |
|               | Any grade |           |   |           |   |           |   |           |   |           |   |           |   |
| Local AE2     | Grade 1   |           |   |           |   |           |   |           |   |           |   |           |   |
|               | Grade 2   |           |   |           |   |           |   |           |   |           |   |           |   |
|               | ...       |           |   |           |   |           |   |           |   |           |   |           |   |
|               | ....      |           |   |           |   |           |   |           |   |           |   |           |   |
| Any local AE* | Grade 1   |           |   |           |   |           |   |           |   |           |   |           |   |
|               | Grade 2   |           |   |           |   |           |   |           |   |           |   |           |   |
|               | Grade 3   |           |   |           |   |           |   |           |   |           |   |           |   |
|               | Any grade |           |   |           |   |           |   |           |   |           |   |           |   |
|               |           |           |   |           |   |           |   |           |   |           |   |           |   |
| Systemic AE1  | Grade 1   |           |   |           |   |           |   |           |   |           |   |           |   |

|                 |         |  |  |  |  |  |  |  |  |  |  |  |  |
|-----------------|---------|--|--|--|--|--|--|--|--|--|--|--|--|
|                 | Grade 2 |  |  |  |  |  |  |  |  |  |  |  |  |
|                 | ...     |  |  |  |  |  |  |  |  |  |  |  |  |
| Any general AE* | Grade 1 |  |  |  |  |  |  |  |  |  |  |  |  |
|                 | Grade 2 |  |  |  |  |  |  |  |  |  |  |  |  |
|                 | ...     |  |  |  |  |  |  |  |  |  |  |  |  |
|                 |         |  |  |  |  |  |  |  |  |  |  |  |  |
| Any AE*         | Grade 1 |  |  |  |  |  |  |  |  |  |  |  |  |
|                 | Grade 2 |  |  |  |  |  |  |  |  |  |  |  |  |
|                 | ...     |  |  |  |  |  |  |  |  |  |  |  |  |

\* List (only) highest grade AE per subject

Clinical Laboratory Data Analysis

- All clinical laboratory abnormalities will be analyzed by participant and will include details of onset time, duration, severity and relationship to the study infusion dose (outcome measure 3).
- Any clinically significant deviations in routine laboratory test results, as determined by the investigator, will be summarized per group (outcome measure 3).
- Isolated laboratory abnormalities will be reported as unsolicited AEs if they are considered clinically relevant by the investigator.

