10.1 Primary study parameter(s)

The number of subjects enrolled, completed, or withdrawn will be summarized. Reasons for withdrawal, when known, will be provided. Demographic data will be summarized by descriptive statistics and will include total number of observations (n), mean, standard deviation (SD) and range for continuous variables, and number and percentages for dichotomous variables. The primary safety, and reactogenicity outcomes will include all subjects who meet the eligibility criteria, receive study product mAb TB31F, and for whom safety data are available.

Safety Analyses

For the safety analysis, data from all subjects who received a dose of mAb TB31F and for whom safety data are available will be included. All analyses will be descriptive. Data will be presented by dose, overall/dose and overall/subject. Results will be summarized by study group. The percentage of subjects with at least one local AE (solicited and unsolicited), with at least one general AE (solicited and unsolicited) and with any AE during the solicited follow-up period will be tabulated with exact 95% CI (two-sided). No multiplicity adjustment will be implemented in analysis. The same calculations will be performed for AEs rated as grade 3. The percentage of subjects reporting each individual solicited local and general AE during the solicited follow-up period will be tabulated with exact 95% CI. The same tabulation will be performed for grade 3 AEs and for AEs with relationship to mAb TB31F administration. The reports of unsolicited AEs will be reviewed by a physician and will be categorized by ICD-10. The percentage of subjects with at least one report of unsolicited AE and reported up to 28 days after mAb TB31F administration will be tabulated with exact 95% CI. The same tabulation will be performed for grade 3 unsolicited AEs and for unsolicited AEs with a relationship to mAb TB31F administration. SAEs will be described in detail. Withdrawals due to AEs/SAEs will also be summarized. Vital signs which are outside of the normal range and clinically significant will also be listed in tables. The frequency of signs and symptoms will be compared between groups with the chi-square test or fishers exact test. Serious adverse events (SAEs) occurring at any point during the trial will be summarized and relatedness to vaccine will be assessed.

Clinical Laboratory Data Analyses

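### The SAP omits the protocol's combined and unsolicited subject-level AE rates, and labels its solicited-only rows 'Any local AE', 'Any general AE' and 'Any AE'

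*SAP*

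**What the plan says.** **Protocol 10.1, Safety Analyses.** The subject-level summaries start with: "The percentage of subjects with at least one local AE (solicited and unsolicited), with at least one general AE (solicited and unsolicited"). The third is any AE: "with any AE during the solicited follow-up period will be tabulated with exact 95% CI (two-sided"). The same calculations are repeated for grade 3. A later sentence in that section adds the percentage of subjects reporting any unsolicited AE up to day 28, again with an exact 95% CI and a grade 3 version.

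**SAP, Safety outcome analyses.** Subjects are tabulated by solicited AE type and grade, and then: "This will also be tabulated for subjects experiencing any solicited local, any solicited general and any solicited AE (see example table below"). The shell is captioned "Table - Descriptive statistics for subjects experiencing solicited AEs". Its summary rows read 'Any local AE', 'Any general AE' and 'Any AE', with the footnote "List (only) highest grade AE per subject".

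For each ICD-10 type of unsolicited AE, "the number of events per dose group and overall study population will be described categorized by severity grade and relation to TB31F administration". The only subject-level line that reaches unsolicited AEs is optional: "The proportion of individuals with grade 1, 2 and 3 adverse events may be compared between groups (Outcome measures 1,2,4"). It does not say whether solicited and unsolicited AEs are pooled.

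**The concern.** The primary objective is safety, and the share of subjects with an AE is a basic tolerability figure. The two documents give it different numerators under nearly the same name. A subject whose only AEs were unsolicited counts in the protocol's rate but not in the SAP's 'Any AE' row. A subject with a grade 1 solicited AE and a higher-grade unsolicited AE has a lower worst grade in the SAP row than under the protocol.

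The excluded events are not trivial in kind. Protocol 9.4.1 solicits only fever, headache, myalgia, fatigue, chills and rash, plus injection-site pain and redness/swelling. The SAP reports clinically relevant isolated laboratory abnormalities as unsolicited AEs. Under protocol 8.3.4 subjects also record bruising and induration, which 9.4.1 does not name as solicited. That bears on group 5, the first subcutaneous use in humans.

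**Working it through.** The plan gives no figure for these rates, so the check is a comparison of definitions followed by bounds.

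**Step 1. Outputs side by side.**

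| Subject-level output | Protocol 10.1 | SAP |
|---|---|---|
| Any local AE | Solicited and unsolicited | Solicited only |
| Any general AE | Solicited and unsolicited | Solicited only |
| Any AE, solicited period | Any AE | Solicited only |
| Any unsolicited AE to day 28 | Yes | No committed output (event counts) |

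The protocol does not repeat the words on solicited and unsolicited for the third row. Following two rows that include both, 'any AE' reads naturally as both.

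**Step 2. Direction.** Let s be the proportion of subjects with a solicited AE in the window and u the proportion with an unsolicited one.

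- SAP rate = s.
- Protocol rate = s + (proportion with unsolicited AEs only), so it is at least s.
- Bounds: max(s, u) ≤ protocol rate ≤ min(1, s + u).

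The rates are equal when every subject with an unsolicited AE also had a solicited one.

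**Step 3. Effect of one subject with only unsolicited AEs.**

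- Group of 5: 1/5 = 20 points. For example, 0/5 (exact 95% CI 0 to 52.2%) becomes 1/5 (0.5 to 71.6%).
- All 25 subjects: 1/25 = 4 points.

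**Step 4. Illustration from the preliminary data (protocol 13.2, groups 1-4).** Fatigue on the dosing day occurred in 12/20 = 60% (exact 95% CI 36.1 to 80.9%). This is a lower limit for any solicited AE. Solicited local AEs occurred in 2/20 = 10% (1.2 to 31.7%). The values of u are assumptions. Under independence the rate is 1 − (1 − s)(1 − u).

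| s | Assumed u | Independence | Bounds |
|---|---|---|---|
| 60% (any AE) | 0% | 60% | 60% |
| 60% | 10% | 64% | 60-70% |
| 60% | 20% | 68% | 60-80% |
| 60% | 50% | 80% | 60-100% |
| 10% (local) | 10% | 19% | 10-20% |
| 10% | 20% | 28% | 20-30% |

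Under independence the gap is (1 − s)u, so it shrinks as s rises. With u = 20% it is 0.40 × 0.20 = 8 points at s = 60%, and 0.20 × 0.20 = 4 points at s = 80%.

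**Step 5. Worst grade.** Take a subject with grade 1 fatigue and a grade 3 laboratory abnormality reported as an unsolicited AE. The any-grade count is the same under both definitions. The protocol's grade 3 count includes the subject; the SAP's grade 3 'Any AE' row does not. This is hypothetical for groups 1-4, where protocol 13.2 reports no grade 3 AEs.

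**The case against.** The case on the other side has five parts.

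- **Scope is stated.** The SAP sentence and the table caption both say solicited. Within that scope the table is correct, and a subject with only unsolicited AEs lies outside it rather than being reported as free of AEs. This stands: the labelling fault is confined to the row names.
- **The SAP follows the endpoints.** Protocol 2.3 and 8.1.1 list solicited local, solicited general and unsolicited AEs separately and define no combined endpoint. This also stands, but 10.1 still commits to the combined rates, and the SAP does not say that it departs from them.
- **Protocol 10.1 may still apply.** The SAP calls itself a supplement and refers to protocol section 10 for confidence intervals. Against this, protocol section 10 says that all data are analysed in accordance with the SAP, which is to supply the table shells. An analyst working from the shell will produce the solicited-only rows.
- **Nothing is concealed.** Unsolicited AEs are reported by type, grade, relatedness and group, SAEs are summarised individually, and protocol 10.1 lists every AE by participant. This stands as to disclosure. What is missing is the planned subject-level summary and its interval.
- **The data may not be ready-made.** The AE details listed in protocol 9.4.3 include no local/general field, so a combined local row needs a classification step. This stands and is part of the fix.

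A reader might infer that the trial's headline AE rate is understated, perhaps by the amounts in the illustration. The documents do not support that. They name no headline rate, the SAP figure is a correct solicited rate, and any gap depends on an unsolicited rate and an overlap that are not given.

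**Conclusion.** The mismatch is real. Followed as written, the SAP does not commit to the three combined subject-level rates or to the unsolicited subject-level rate that protocol 10.1 specifies, and its row labels suggest wider coverage than the rows have. The SAP rows equal the protocol-defined rates or are lower, never higher. They are lower whenever a subject has only unsolicited AEs in the window, by 20 points per such subject in a group of 5, and the worst grade can be lower even when the rates agree.

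The total gap cannot be computed and may be zero; the figures in step 4 are illustrations under assumed unsolicited rates. The conclusion rests only on the two texts and on reading the protocol's 'any AE' as covering both kinds. It should be put right before database lock, but it is an inconsistency between planned outputs, not evidence of a biased safety result.

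**What to change.** In the SAP's safety text and table shell:

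1. Relabel the existing rows 'Any solicited local AE', 'Any solicited general AE' and 'Any solicited AE'.
2. Add combined rows (solicited plus unsolicited) for local, general and any AE, by worst grade per subject, with exact 95% CIs.
3. Add a row for subjects with any unsolicited AE to day 28, also by worst grade and with an exact 95% CI.
4. State the window for each row: day 7 for local, day 28 for general and any AE, in line with protocol 9.4.2. Protocol 10.1 speaks only of the solicited period, and that period differs between local and general AEs.
5. State how each unsolicited AE is classified as local or general for these rows.

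If the solicited-only summary was intended, record and justify the departure from protocol 10.1 instead, and still make change 1.

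The cost is a few more table rows and a short classification step on AEs that are already recorded. The reported AE rate may come out higher.

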If an adverse event changes in intensity during the specified reporting period, a new description of the adverse event will be added. Interrupted AEs are registered as one AE if the interruption is <24 hours. When an AE/SAE occurs, it is the responsibility of the investigators to review all documentation (e.g. hospital progress notes, laboratory, and diagnostics reports) related to the event. The investigators will then record all relevant information regarding an AE/SAE on the CRF or SAE Report Form, respectively.

The investigator will attempt to establish a diagnosis of the event based on signs, symptoms and/or other clinical information. In such cases, the diagnosis should be documented as the AE/SAE and not the individual signs/symptoms.

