### Sample size

Sample size calculations are based on assessing safety parameters. A total of twenty-five healthy adults (males and females) aged 18 – 35 will be divided over four groups. Each group will include five subjects. With the study's original sample size of n=20 (four intravenous groups of n=5), there is a 90% chance of observing at least 1 event if the true rate of such an event is 10.87% or more; and there is a 90% chance of observing no events if the true rate is 0.52% or less. The 5th (subcutaneous) group was pragmatically chosen to have the same size. Sample size for each group is appropriate for mAb infusion phase 1 trials based on similar trial designs for HIV, CMV, and anthrax monoclonal antibody prophylactic studies. Comparisons of the occurrence of adverse events and efficacy endpoints (e.g. antibody prevalence, density and transmission reducing activity) between study arms will be performed but the study is not specifically powered for this. Instead, TB31F pharmacokinetic parameters will be assessed by standard non-compartmental methods, using multiple observations per group and per study participant, and related to functional transmission reducing activity estimates (TRA).

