## Statistical Principles

### Confidence intervals and P values

Confidence intervals and P values are specified in protocol section 10 and will be based on 0.05 as significance level. Adjustments for multiple comparisons will be implemented where appropriate. Where applicable, normally distributed continuous outcomes will be presented as mean with 95% CI or standard deviations. Continuous outcomes that are not normally distributed will be transformed using a suitable transformation before reporting 95% CIs. Where a suitable transformation cannot be found, medians will be presented with interquartile ranges. For discrete (or count) data we will find interquartile ranges. Binary data will be presented as counts and proportions.

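### Where each subject is counted only at the highest AE grade, a group comparison on the grade 1 row can favour the more harmful dose; use cumulative grades or one ordinal test instead

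*SAP*

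**What the plan says.** The SAP (Safety outcome analyses) tabulates, for each solicited AE type, the subjects affected by severity grade and dose group, and does the same for any solicited local, any solicited general and any solicited AE. It then says: "Where applicable, we will compare these proportions between groups". A later bullet, which extends to unsolicited AEs, adds: "The proportion of individuals with grade 1, 2 and 3 adverse events may be compared between groups (Outcome measures 1,2,4".

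The example table is headed "Table - Descriptive statistics for subjects experiencing solicited AEs". Its footnote reads "List (only) highest grade AE per subject" and is attached by an asterisk to three blocks only: Any local AE, Any general AE and Any AE. The blocks for single AE types carry no asterisk. The table shows rows for grades 1, 2 and 3 and an any-grade row. It has no grade 2 or higher row.

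Protocol 10.1 names the tests: "The frequency of signs and symptoms will be compared between groups with the chi-square test or fishers exact test". It also tabulates subjects with at least one AE, and grade 3 AEs, with exact confidence intervals. On size and level, the SAP says "Each group will include five subjects" and that P values "will be based on 0.05 as significance level".

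**The concern.** The primary endpoint covers the number and the severity of AEs, so a severity comparison should ask whether one dose group has worse AEs than another. In the three footnoted blocks, the grade 1 row holds subjects whose worst AE was exactly grade 1. A subject whose worst AE becomes grade 2 leaves that row. Fewer subjects in the grade 1 row can therefore mean less harm or more harm, and a p-value on that row cannot tell which.

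Two things follow. A significant result in the grade 1 row may appear to favour the more harmful dose. The rise it mirrors may also be divided between the grade 2 and grade 3 rows, where each test sees only part of it. The any-grade row does not help when the same number of subjects is affected but more severely. Neither document plans a grade 2 or higher comparison or an ordinal one.

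**Working it through.** **Inputs.** Five per group (SAP, Sample size); level 0.05 (SAP, Confidence intervals and P values); chi-square or Fisher's exact test (Protocol 10.1), with Fisher used here because of the group size. Sidedness is not stated for these tests, so two-sided is assumed. Protocol 13.2 reports fatigue of grade 1 or 2 in 12 of 20 subjects in groups 1–4 (60%) and no grade 3 AE. Grade distributions by group are not given, so those below are assumptions.

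**The plan's own figure.** No figure is given for these comparisons. The sample-size statement does reproduce: 1 − (1 − 0.1087)^20 = 0.900 and (1 − 0.0052)^20 = 0.901. It concerns seeing any event in 20 subjects, not comparing groups.

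**Which 5 v 5 tables are significant.** Only three splits reach p ≤ 0.05:
- 5 v 0: p = 2/252 = 0.008
- 4 v 0: p = 2 × 5/210 = 0.048
- 5 v 1: p = 0.048, by symmetry

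**One data example.** Low dose: four subjects at grade 1, one with no AE. High dose: two at grade 2, two at grade 3, one with no AE.
- Grade 1: 4 v 0, p = 0.048, fewer at the high dose
- Grade 2: 0 v 2, p = 0.444
- Grade 3: 0 v 2, p = 0.444
- Any grade: 4 v 4, p = 1.0
- Grade 2 or higher: 0 v 4, p = 0.048, more at the high dose

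With three of five affected in each group (three at grade 1 v two at grade 2 and one at grade 3), the grade 1 and the grade 2 or higher comparisons both give p = 0.167, so nothing is significant.

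**How often it happens.** Let p be the probability of falling in a row in the group with the larger true proportion, and q that in the other group. The chance of a significant difference in that direction is

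P = p^5 [(1 − q)^5 + 5q(1 − q)^4] + 5p^4(1 − p)(1 − q)^5.

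For grade 1 at 50% (low dose) v 10% (high dose): 0.03125 × 0.91854 + 0.15625 × 0.59049 = 0.029 + 0.092 = 0.121. The other entries use the same formula.

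| Low dose, worst grade 1/2/3 (%) | High dose, worst grade 1/2/3 (%) | Grade 1 row: fewer at high dose | Grade 2 row: more | Grade 3 row: more | Grade ≥2: more |
|---|---|---|---|---|---|
| 50/10/0 | 30/30/0 | 4% | 2% | 0% | 2% |
| 50/10/0 | 10/50/0 | 12% | 12% | 0% | 12% |
| 50/10/0 | 10/30/20 | 12% | 2% | 1% | 12% |
| 60/0/0 | 10/30/20 | 22% | 3% | 1% | 19% |
| 60/0/0 | 0/35/25 | 34% | 5% | 2% | 34% |
| 60/0/0 | 0/60/0 | 34% | 34% | 0% | 34% |
| 80/10/0 | 10/60/20 | 54% | 22% | 1% | 54% |
| 80/0/0 | 10/50/30 | 54% | 19% | 3% | 74% |

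The first six lines hold the overall rate at 60% in both groups; there the any-grade row is significant in either direction less than 1% of the time. The last two lines are deliberately more extreme. Where no grade 3 events occur, the grade 2 row and grade 2 or higher are the same row, so no power is lost; the grade 1 reversal remains.

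**Multiplicity.** Protocol 10.1 plans no adjustment; the SAP plans one where appropriate. With Bonferroni over the 10 group pairs the threshold is 0.005, below the smallest attainable 0.008, so no pairwise table could be significant in either direction.

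**The case against.** The strongest reply is that the plan does not commit to row-by-row tests. The SAP wording also allows one test of the whole grade distribution. On the two extreme scenarios, an exact test over none/1/2/3 rejects in 56% and 68%, against 54% and 74% for grade 2 or higher. On that reading the loss of power largely disappears. This stands, but such a test has no direction, and the SAP does not say that it is the one intended.

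Much of the remedy is also already there. Any-grade and grade 3 tabulations are planned, and grade 2 or higher is the sum of two printed rows. A reader would see the grade 2 and 3 counts directly below the grade 1 row. Protocol 10.1 calls the safety analyses descriptive, one of the two SAP sentences is optional, and the SAP says that the study is not powered for comparisons between arms. Escalation rests on SMC review and the holding rules (Protocol 9.5.3 and 9.5.4), not on these p-values. All of this stands and lowers the weight of the point. It does not make a p-value on the exclusive grade 1 row interpretable.

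A reader might infer that the highest-grade rule governs every by-grade comparison, including unsolicited AEs (outcome measure 4). The documents do not support that: the footnote covers three blocks of a solicited-AE table. Protocol 9.4.3 also says "If an adverse event changes in intensity during the specified reporting period, a new description of the adverse event will be added", so one subject may have entries at several grades. For single AE types and unsolicited AEs, the gap is that no counting rule is stated.

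**Conclusion.** The point holds for the Any local AE, Any general AE and Any AE rows if they are compared row by row. There the grade 1 comparison can point the wrong way, and the any-grade row cannot show a pure shift in severity. At a 60% event rate the reversal occurs in about 12–34% of trials under marked assumed shifts and 4% under a milder one; under more extreme severities it reaches 54%. These figures rest on assumed grade distributions, 5 v 5 two-sided Fisher tests and no multiplicity adjustment.

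Two stronger readings go too far. One is that a more toxic dose will show significantly fewer grade 1 AEs: with five per group this needs a split of 5 v 1, 4 v 0 or 5 v 0, and in most of the 60% scenarios it usually does not happen. The other is that harm is always split over two rows: that needs grade 3 events, and Protocol 13.2 reports none in groups 1–4, so a split would require them in group 5 or in AEs arising after that update.

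Rating: consider. The comparisons are unpowered and do not drive dose escalation.

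**What to change.** In the SAP's Safety outcome analyses:
- State that, for every between-group severity comparison (single AE types, the three any-AE blocks and unsolicited AEs), each subject counts once, at the worst grade.
- Compare cumulative proportions: any grade, grade 2 or higher, grade 3 or higher. Alternatively, use one exact ordinal test on each subject's worst grade, with no AE as the lowest category. Name the choice in advance.
- Keep the exclusive grade 1, 2 and 3 rows as description, without p-values.

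The cost is a few sentences; no new data are needed and the table can stay as it is. The cumulative categories overlap, so their results are not independent. The ordinal test is a single test but is not always sharper: in the data example above, an exact rank-sum test gives p = 0.143 against 0.048 for grade 2 or higher. Neither choice gives the study useful power at five per group; the gain is that a significant result points in the right direction.
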